4.7 Secondary outcomes

Secondary outcomes will be analyzed in the ITT population. Continuous variables (e.g., operation time, estimated blood loss, distance from anastomosis to anal verge, length of postoperative hospital stay, hospitalization cost, quality of life score) will be compared using the Student's t-test (for normally distributed data) or Wilcoxon rank-sum test (for non-normally distributed data), with the median difference and corresponding 95% confidence interval reported. For categorical variables (e.g., surgical approach, surgical type, anastomotic technique, overall/mild/severe complication rate, Clavien-Dindo grade), the two-

sided Pearson's χ^2 test or Fisher's exact test will be used as appropriate (see appendix Table 4).

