Statistical Analysis Plan (Final, Version 1.2)

Principal Investigator: [name]

Research Institution: Sir Run Run Shaw Hospital, Zhejiang University

Register Number: NCT06204497

Date: 2025-10-26

Version: 1.2

Statistical Analysis Plan Authors: [name]

Department of Epidemiology and Biostatistics, Zhejiang University

School of Medicine, China

E-mail: [contact]

1. Introduction

This trial is a multicenter, prospective, randomized, controlled, open label, parallel-group, non-inferiority trial to evaluate the safety and efficacy of stent-based diverting technique (SDT) versus ileostomy in rectal cancer patients. In this trial, SDT is considered to reduce the overall length of post-operation hospital stay and medical costs, improve patients' quality of life, while not increasing the peri-operative complication rate. The primary outcome was the 90-day incidence of severe complications (Clavien-Dindo grade \geq III). Secondary outcomes included overall complication rate, anastomotic leakage rate (grade B/C), length of postoperative hospital stay, hospitalization costs, and 90-day postoperative quality of life.

Patients were randomized 1:1 to two groups:

- SDT group: rectal cancer surgery plus stent-based diverting technique
- Ileostomy group: rectal cancer surgery plus protective ileostomy

Follow-up concluded 90 days after the last patient underwent surgery.

2. Population

● 2.1 Intent-to-treat population

The intent-to-treat (ITT) population will include all randomized participants, with grouping according to their originally assigned treatment,

regardless of whether the allocated intervention was actually received or completed. Primary and secondary outcome analyses will be performed in the intent-to-treat (ITT) population. As randomization was performed intraoperatively, a modified ITT (mITT) population was not defined in this study.

- **2.2 Per-protocol population**

The per-protocol (PP) population includes all randomized participants who completed the study as planned, with no major protocol violations, adequate adherence to the assigned intervention, and sufficient follow-up data for the primary outcome assessment. Primary and secondary outcome analyses will be conducted in the PP population as sensitivity analyses.

- **2.3 As-treated population**

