4.2 General calculations

For the summary of population characteristics, all percentages will be calculated with the total number of the intent-to-treat (ITT) population as the denominator (including all patients with missing data for the relevant variable). For the summary of categorical outcome variables (e.g., complication rate), patients with missing data will be excluded from the denominator when calculating percentages. For the summary of continuous outcome variables (e.g., estimated blood loss, length of hospital stay, cost), patients with missing data will be excluded when calculating means or medians. When patients with missing data are excluded from the denominator, the number of patients included in the summary will be clearly reported.

All percentages, means, standard deviations (SDs), medians, interquartile ranges (IQRs), and ranges will be rounded to 2 decimal place. P-values will be rounded to 3 decimal places. Parameter estimates, standard errors (SEs), relative ratios (RRs), and 95% confidence intervals (CIs) will be reported to 2 decimal places. The primary outcome will be performed one-sided at $\alpha = 0.025$, with results presented as treatment differences and corresponding 97.5% one-sided confidence intervals. Other comparisons will be two-sided at $\alpha = 0.05$, with 95% two-sided confidence intervals reported.

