4.6 Primary outcome

The primary endpoint will be analyzed in the ITT population and defined as the rate of severe complications (Clavien-Dindo grade \geq III) within 90 days post-surgery, the primary endpoint will be assessed as follows (Time Frame: For the Study Group, from the SDT to 90 days after surgery; if the patient undergoes ileostomy as a salvage procedure, the time frame will be extended to 90 days after stoma reversal. For the Control Group, from ileostomy creation to 90 days after stoma reversal. For patients in

both groups who do not undergo stoma reversal, the time frame will be defined as 90 days after the initial surgery).

The primary non-inferiority analysis will be based on the risk difference (RD) with a predefined non-inferiority margin of 2.8%. The RD and its 97.5% one-sided confidence interval will be estimated using binomial regression with identity link. For the relative risk (RR), binomial regression with log link will be used to estimate the RR and two-sided 95% confidence interval. The RR is reported as a supplementary effect measure and will not be used for the non-inferiority test ((see appendix Table 2).

Non-inferiority margin justification: The non-inferiority margin of 2.8% was determined based on clinical relevance and pilot data. This margin was defined such that the severe complication rate in the SDT group would not exceed 120% of that in the ileostomy group (i.e., a 20% relative increase). Given the expected severe complication rate of 14% in the ileostomy group in our pilot study, the absolute non-inferiority margin was calculated as $14\% \times 0.2 = 2.8\%$. In clinical practice, an absolute increase of no more than 2.8% in severe complications is considered acceptable, as it is negligible compared with the substantial benefits of SDT: avoidance of stoma creation and reversal, shorter hospital stay, lower medical costs, and improved quality of life.

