Number of high-risk factors, No. (%)		
Single	XX (XX)	XX (XX)
Multiple	XX (XX)	XX (XX)
Pathological TNM stage, No. (%)		
0	XX (XX)	XX (XX)
I	XX (XX)	XX (XX)
II	XX (XX)	XX (XX)
III	XX (XX)	XX (XX)

Table 2

Outcomes	Stent-based Diverting Technique (n=)	Ileostomy (n=)	P value
Primary outcome			
Events (severe complications), No	XX	XX	
Incidence of severe complications, % (95% CI)*	XX (95% CI, XX– XX)	XX (95% CI, XX– XX)	
Between-group difference in incidence, % (97.5% CI)	-XX (–∞, XX%)	-	XX
Relative ratio, % (95% CI)*	XX (XX–XX)	-	XX
Secondary outcomes			
Incidence of total complications, No. (%)*	XX (XX)	XX (XX)	XX
Incidence of mild complications, No. (%)*	XX (XX)	XX (XX)	XX
Complications (Events)	XX (XX)	XX (XX)	-
General complications, No. (%)	XX (XX)	XX (XX)	-
Anastomotic leakage (Grade B)	XX (XX)	XX (XX)	XX
Anastomotic leakage (Grade C)	XX (XX)	XX (XX)	XX
Anastomotic stenosis	XX (XX)	XX (XX)	XX
Intestinal obstruction	XX (XX)	XX (XX)	XX
Intestinal perforation	XX (XX)	XX (XX)	XX
Abdominal infection	XX (XX)	XX (XX)	XX
Bleeding	XX (XX)	XX (XX)	XX
Others†	XX (XX)	XX (XX)	XX
Stent or Tube-related complications, No. (%)	XX (XX)	XX (XX)	-
Stent displacement	XX (XX)	XX (XX)	-
Intestinal fistula‡	XX (XX)	XX (XX)	-
Mushroom-shaped tube-related dermatitis	XX (XX)	XX (XX)	-
Mushroom-shaped tube displacement	XX (XX)	XX (XX)	-
Stoma-related complications, No. (%)	XX (XX)	XX (XX)	-

Parastomal hernia	XX (XX)	XX (XX)	-
Dermatitis	XX (XX)	XX (XX)	-
Stoma obstruction	XX (XX)	XX (XX)	-
Stoma bleeding	XX (XX)	XX (XX)	-
Grade of complications			
I	XX (XX)	XX (XX)	XX
II	XX (XX)	XX (XX)	XX
III	XX (XX)	XX (XX)	XX
IV	XX (XX)	XX (XX)	XX
V§	XX (XX)	XX (XX)	XX
Converse to Stent-based Diverting Technique, No. (%)	-	XX (XX)	-
Converse to ileostomy, No. (%)	XX (XX)	-	-
Converse to salvage ileostomy, No. (%)	XX (XX)	-	-
Time of stent degradation			
No stent	XX (XX)	XX (XX)	-
Stent displacement	XX (XX)	XX (XX)	-
Before 3 weeks	XX (XX)	XX (XX)	-
3-4 weeks	XX (XX)	XX (XX)	-
5-6 weeks	XX (XX)	XX (XX)	-
Stoma ending, No. (%)#			
No stoma	XX (XX)	XX (XX)	-
Reversal on time (stage II)	XX (XX)	XX (XX)	-
Delayed reversal	XX (XX)	XX (XX)	-

Table 3

	Stent-based Diverting Technique	Ileostomy	P value
PHS and Costs	n=	n=	
Unplanned readmission, No. (%)	XX ± XX	XX ± XX	XX
PHS (stage I), days	XX ± XX	XX ± XX	XX
PHS (stage II), days	XX ± XX	XX ± XX	XX
PHS (Readmission),	XX ± XX	XX ± XX	XX
Total PHS, days*	XX ± XX	XX ± XX	XX
Total PHS (Only patients with reversal), days*	XX ± XX	XX ± XX	XX

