Cost (stage I), CNY	XX ± XX	XX ± XX	XX
Cost (stage II), CNY	XX ± XX	XX ± XX	XX
Cost (Readmission), CNY	XX ± XX	XX ± XX	XX
Total Cost, CNY*	XX ± XX	XX ± XX	XX
Total Cost (Only patients with reversal), CNY*	XX ± XX	XX ± XX	XX
Quality of life	n=	n=	
General Health*	XX ± XX	XX ± XX	XX
Physical Function*	XX ± XX	XX ± XX	XX
Role-Physical*	XX ± XX	XX ± XX	XX
Bodily Pain*	XX ± XX	XX ± XX	XX
Vitality*	XX ± XX	XX ± XX	XX
Social Functioning*	XX ± XX	XX ± XX	XX
Mental Health*	XX ± XX	XX ± XX	XX
Role-Emotional*	XX ± XX	XX ± XX	XX

Subgroup	Level	Events/total SDT	SDT_95%CI	Events/total ILE	ILE_95%CI	RD 97.5%CI	RR	Interaction_p
Age	<60	XX/XX	XX (XX–XX)	XX/XX	XX (XX–XX)	XX (-∞–XX)	XX (XX-XX)	XX
Age	≥60	XX/XX	XX (XX–XX)	XX/XX	XX (XX–XX)	XX (-∞–XX)	XX (XX-XX)	XX
Gender	Female	XX/XX	XX (XX–XX)	XX/XX	XX (XX–XX)	XX (-∞–XX)	XX (XX-XX)	XX
Gender	Male	XX/XX	XX (XX–XX)	XX/XX	XX (XX–XX)	XX (-∞–XX)	XX (XX-XX)	XX
Body_mass_index	<24.0	XX/XX	XX (XX–XX)	XX/XX	XX (XX–XX)	XX (-∞–XX)	XX (XX-XX)	XX
Body_mass_index	≥24.0	XX/XX	XX (XX–XX)	XX/XX	XX (XX–XX)	XX (-∞–XX)	XX (XX-XX)	XX
Diabetes	N	XX/XX	XX (XX–XX)	XX/XX	XX (XX–XX)	XX (-∞–XX)	XX (XX-XX)	XX
Diabetes	Y	XX/XX	XX (XX–XX)	XX/XX	XX (XX–XX)	XX (-∞–XX)	XX (XX-XX)	XX
Noeoadjuvant_radiotherapy	N	XX/XX	XX (XX–XX)	XX/XX	XX (XX–XX)	XX (-∞–XX)	XX (XX-XX)	XX
Noeoadjuvant_radiotherapy	Y	XX/XX	XX (XX–XX)	XX/XX	XX (XX–XX)	XX (-∞–XX)	XX (XX-XX)	XX
Tumor_to_anal_verge	<7	XX/XX	XX (XX–XX)	XX/XX	XX (XX–XX)	XX (-∞–XX)	XX (XX-XX)	XX

Tumor_to_anal_verge	≥ 7	XX/XX	XX (XX-XX)	XX/XX	XX (XX-XX)	XX (-∞-XX)	XX (XX-XX)	XX
Number_of_high_risk_factors	Single	XX/XX	XX (XX-XX)	XX/XX	XX (XX-XX)	XX (-∞-XX)	XX (XX-XX)	XX
Number_of_high_risk_factors	Multiple	XX/XX	XX (XX-XX)	XX/XX	XX (XX-XX)	XX (-∞-XX)	XX (XX-XX)	XX
Prior_abdominal_surgery	N	XX/XX	XX (XX-XX)	XX/XX	XX (XX-XX)	XX (-∞-XX)	XX (XX-XX)	XX
Prior_abdominal_surgery	Y	XX/XX	XX (XX-XX)	XX/XX	XX (XX-XX)	XX (-∞-XX)	XX (XX-XX)	XX
Pathological_T_stage	0-2	XX/XX	XX (XX-XX)	XX/XX	XX (XX-XX)	XX (-∞-XX)	XX (XX-XX)	XX
Pathological_T_stage	3-4	XX/XX	XX (XX-XX)	XX/XX	XX (XX-XX)	XX (-∞-XX)	XX (XX-XX)	XX
Pathological_N_stage	Negative	XX/XX	XX (XX-XX)	XX/XX	XX (XX-XX)	XX (-∞-XX)	XX (XX-XX)	XX
Pathological_N_stage	Positive	XX/XX	XX (XX-XX)	XX/XX	XX (XX-XX)	XX (-∞-XX)	XX (XX-XX)	XX
Centers	Low-volume	XX/XX	XX (XX-XX)	XX/XX	XX (XX-XX)	XX (-∞-XX)	XX (XX-XX)	XX
Centers	High-volume	XX/XX	XX (XX-XX)	XX/XX	XX (XX-XX)	XX (-∞-XX)	XX (XX-XX)	XX

Statistical Analysis Plan (Modified Version 1.1)

Principal Investigator: [name]

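### For stay, cost and quality of life, the test, the reported estimate and the Table 3 layout do not match, and no comparison of mean cost is planned if cost is judged non-normal

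*SAP*

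**What the plan says.** **Test and estimate.** SAP section 4.7 applies one rule to all continuous secondary outcomes, including "length of postoperative hospital stay, hospitalization cost, quality of life score". Normally distributed data go to Student's t-test and other data to the Wilcoxon rank-sum test. The sentence ends "with the median difference and corresponding 95% confidence interval reported", and by its wording this covers both tests. It names no criterion for normality and no method for the interval around the median difference.

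**Table.** In appendix Table 3 the rows for stay, cost and quality of life, among them "Total PHS, days" and "Total Cost, CNY", have one XX ± XX cell per arm and a P value. Table 3 does not say what the ± means; Table 1 labels the same format as mean and SD. Table 3 has no column for a median, a difference or a confidence interval. Section 4.7 refers the reader to appendix Table 4, but no table in the text at hand carries that label.

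**Role of cost.** The introduction presents lower medical cost and shorter overall stay as expected effects of SDT. Section 4.6 lists "shorter hospital stay, lower medical costs, and improved quality of life" among the benefits that make a 2.8% absolute increase in severe complications acceptable.

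**The concern.** Three quantities are combined without a link between them: the hypothesis tested, the effect estimated and the summary tabulated. A reader of Table 3 will see two means and a P value and take the P value as a test of those means. On the Wilcoxon route it is not.

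For cost this could affect the conclusion. A statement that SDT lowers medical cost overall concerns the arithmetic mean, because mean cost times the number of patients is what is spent. A rank test and a median describe the typical patient instead. The two can diverge when one arm has a low typical cost and a costly minority. The SAP itself gives reasons to consider that pattern: SDT avoids a planned stoma and its reversal, but some SDT patients need a salvage ileostomy (section 4.6), and readmission cost has its own row in Table 3.

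**Working it through.** **1. What each route would report.**

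| Route | P value concerns | Estimate under 4.7 | Shown in Table 3 |
|---|---|---|---|
| t-test | difference in means | median difference, 95% CI | XX ± XX and P |
| Wilcoxon | ordering of the two distributions | median difference, 95% CI | XX ± XX and P |

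In the first row, test and estimate differ. In the second, the P value does not test the tabulated means. In neither row does the table have a place for the promised estimate. This step needs no assumption about the data.

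**2. Inputs for the size.** The SAP gives no cost, SD or sample size, so it has no figure on this point to reproduce. From the SAP come two-sided alpha 0.05 (section 4.2) and 1:1 allocation (introduction). The following are assumptions:

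- 14% of patients in each arm have a complicated course. The SAP expects 14% severe complications with ileostomy; using it for both arms is assumed.
- True mean cost is m = 76.9 thousand in both arms.
- A complicated course adds a premium P, so the uncomplicated cost is m − 0.14 × P.
- Noise is lognormal with log-scale SD sigma of 0.2, 0.35 or 0.5.
- There are 150, 250 or 400 patients per arm.

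**3. Equal means by construction** (thousands).

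- SDT premium 85: 76.9 − 0.14 × 85 = 65.0 uncomplicated and 150.0 complicated. Check: 0.86 × 65.0 + 0.14 × 150.0 = 55.9 + 21.0 = 76.9.
- Ileostomy premium 20: 76.9 − 0.14 × 20 = 74.1 and 94.1. Check: 63.7 + 13.2 = 76.9.
- Milder contrast, 60 v 30: SDT 68.5 and 128.5; ileostomy 72.7 and 102.7.
- No contrast, 50 v 50: 69.9 and 119.9 in both arms.

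**4. Wilcoxon rejection with equal true means** (1,000 trials per cell, n = 150 / 250 / 400 per arm).

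| Premium, SDT v ileostomy | sigma 0.2 | sigma 0.35 | sigma 0.5 |
|---|---|---|---|
| 85 v 20 | 92 / >99 / 100% | 34 / 53 / 74% | 18 / 26 / 36% |
| 60 v 30 | 32 / 47 / 69% | 11 / 13 / 20% | 7 / 7 / 11% |
| 50 v 50 | 4–6% over the cells run | | |

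A separate run gave 15–100% for 85 v 20 and 6–68% for 60 v 30. Differences of a few points are simulation error: at 50% the standard error is √(0.25/1000) = 1.6 points. Welch's test on the mean stayed at 4–6%. With 85 v 20 and sigma 0.2, the median difference averaged −8.4 thousand in favour of SDT although the means were equal.

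**5. A second parameterisation.** Here the ileostomy arm is lognormal with mean 100 and CV 0.3. A fraction q of SDT patients costs R times the rest, and the SDT mean is also 100. The section 4.7 rule was coded with a Shapiro-Wilk check, which is an assumption; it chose Wilcoxon in 98–100% of trials. The table gives the share of trials that show a significant SDT advantage.

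| Setting | n = 100 | n = 200 | n = 300 |
|---|---|---|---|
| q 10%, R 3 | 71% | 95% | 99% |
| q 5%, R 3 | 34% | 59% | 73% |
| q 10%, R 2 | 16% | 28% | 39% |

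With CV 0.5 and n = 200 (q 10%), the share is 12% for R = 2 and 48% for R = 3. With the same distribution in both arms it is about 3%. For q 10%, R 3 and CV 0.3 the population medians are 83 and 96, a gap of 13 that is absent from the means. Welch shows an SDT advantage in 2–5% of trials across all settings, against a nominal 2.5%.

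**The case against.** The strongest reply is that Wilcoxon does nothing wrong here. In these scenarios the typical SDT patient really is cheaper, so the test detects a true difference between distributions. This stands: the result is an answer to another question, not a false positive.

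It can also be said that the large percentages come from one demanding choice of costs, an SDT premium 85/20 = 4.25 times that of ileostomy with little noise, for which the documents give no support. This stands too, which is why the whole range is shown.

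Third, the totals in Table 3 follow rows for stage I, stage II and readmission, so they appear to be sums within a patient. A median of such a sum is a legitimate target, particularly for stay. This stands for stay and quality of life, where mean or median is a matter of choice and the defect is only the mismatch.

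Fourth, printed means would let a reader notice that mean costs are equal. This helps only in part, because the P value beside them invites the opposite reading.

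Finally, these are secondary outcomes and do not enter the non-inferiority decision, which rests on the risk difference. That limits the weight of the point but does not remove the inconsistency.

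**Conclusion.** The mismatch between section 4.7 and Table 3 follows from the text alone, with one caveat: the ± in Table 3 is read as mean and SD by analogy with Table 1. The template is loose, since it also gives a row headed as number and percentage in the ± format.

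For total cost, the plan has no comparison of means if the data are judged non-normal, so it could not by itself support a claim of lower overall cost. How far this could mislead depends on assumed costs. With equal true means and 150 to 400 patients per arm, Wilcoxon rejects in about 5% of trials with equal premiums, 6–68% with 60 v 30 and 15–100% with 85 v 20, against 4–6% for Welch.

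A reader might infer that the plan will declare a saving that does not exist, or that a formal normality pre-test is prescribed and should be struck out. The documents support neither. The divergence requires arms of different shape, skewness of cost is plausible but not documented, and section 4.7 mentions normality without describing a test. The point should be corrected, but it does not threaten the primary conclusion.

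**What to change.** - **Total cost:** prespecify the difference in arithmetic means, SDT minus ileostomy, with a Welch or bootstrap 95% CI and the P value from the same method, whatever the shape of the data. Give median and IQR descriptively.
- **Stay and quality of life:** choose one estimand for each, mean or median, and name the test, estimate and interval method that belong to it.
- **Table 3:** label the per-arm summary, add a column for the estimate with its 95% CI, and correct the reference to Table 4 in section 4.7.

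The cost is a few sentences of SAP text and minor programming, with no new data. The downside is a somewhat wider interval for cost if it is skewed.

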4.8 Sensitivity analysis

Sensitivity analyses will be conducted for the PP and AT populations. Sensitivity models will replicate the primary analysis to ensure consistency across populations. The statistical methods used in these sensitivity analyses will be consistent with those applied to the ITT population. Results will be compared and interpreted across the ITT, PP, AT populations to determine whether protocol violations or missing data have an impact on the study outcomes.

5. Safety monitoring

Safety indicators will be monitored and analyzed in the safety population. Each participating medical center will designate independent monitors to oversee safety indicators, including the postoperative severe complication rate and serious adverse events.

To ensure participant safety and trial rigor, an independent DSMB was composed of a colorectal surgeon, a biostatistician, and an ethics consultant. The DSMB conducted blinded reviews (with no access to group allocation) of the primary outcome: the incidence of 90-day severe complications (Clavien-Dindo grade \geq III) and all serious adverse events (SAEs) every 6 months. During these reviews, no protocol violations or safety signals

warranting trial suspension were identified, and the DSMB consistently recommended that the trial continue as planned.

6. Appendix tables

Table 1

Characteristics	Stent-based Diverting Technique (n=)	Ileostomy (n=)
Age, y		
Mean ± SD	XX ± XX	XX ± XX
Group, No. (%)		
< 60	XX (XX)	XX (XX)
≥60	XX (XX)	XX (XX)
Gender, No. (%)		
Male	XX (XX)	XX (XX)
Female	XX (XX)	XX (XX)
Body mass index*		
Mean ± SD, kg/m2	XX (XX)	XX (XX)
Group, No. (%)		
<18.5 (Underweight)	XX (XX)	XX (XX)
18.5-23.9 (Normal)	XX (XX)	XX (XX)
≥24.0 (Overweight/Obese)	XX (XX)	XX (XX)
Smoking	XX (XX)	XX (XX)
Drinking	XX (XX)	XX (XX)
Concomitant, No. (%)		
Hypertension	XX (XX)	XX (XX)
Diabetes	XX (XX)	XX (XX)
Cardiovascular system diseases	XX (XX)	XX (XX)
Respiratory system diseases	XX (XX)	XX (XX)
Urinary system diseases	XX (XX)	XX (XX)

ASA classification, No. (%)†		
I (Healthy)	XX (XX)	XX (XX)
II (Mild systemic disease)	XX (XX)	XX (XX)
III (Severe systemic disease)	XX (XX)	XX (XX)
Eastern cooperative oncology group score		
0	XX (XX)	XX (XX)
1	XX (XX)	XX (XX)
Prior abdominal surgery, No. (%)	XX (XX)	XX (XX)
High-risk factors of anastomosis leakage, No. (%)		
Neoadjuvant radiotherapy	XX (XX)	XX (XX)
Tumor to anal verge≤7cm	XX (XX)	XX (XX)
Intraoperative factors‡	XX (XX)	XX (XX)
Others§	XX (XX)	XX (XX)
Number of high-risk factors, No. (%)		
Single	XX (XX)	XX (XX)
Multiple	XX (XX)	XX (XX)
Pathological TNM stage, No. (%)		
0	XX (XX)	XX (XX)
I	XX (XX)	XX (XX)
II	XX (XX)	XX (XX)
III	XX (XX)	XX (XX)

Table 2

Outcomes	Stent-based Diverting Technique (n=)	Ileostomy (n=)	P value
Primary outcome			
Events (severe complications), No	XX	XX	
Incidence of severe complications, % (95% CI)*	XX (95% CI, XX– XX)	XX (95% CI, XX– XX)	
Between-group difference in incidence, % (97.5% CI)	-XX (–∞, XX%)	-	XX
Relative ratio, % (95% CI)*	XX (XX–XX)	-	XX
Secondary outcomes			
Incidence of total complications, No. (%)*	XX (XX)	XX (XX)	XX
Incidence of mild complications, No. (%)*	XX (XX)	XX (XX)	XX
Complications (Events)	XX (XX)	XX (XX)	-
General complications, No. (%)	XX (XX)	XX (XX)	-
Anastomotic leakage (Grade B)	XX (XX)	XX (XX)	XX
Anastomotic leakage (Grade C)	XX (XX)	XX (XX)	XX
Anastomotic stenosis	XX (XX)	XX (XX)	XX
Intestinal obstruction	XX (XX)	XX (XX)	XX
Intestinal perforation	XX (XX)	XX (XX)	XX
Abdominal infection	XX (XX)	XX (XX)	XX
Bleeding	XX (XX)	XX (XX)	XX
Others†	XX (XX)	XX (XX)	XX
Stent or Tube-related complications, No. (%)	XX (XX)	XX (XX)	-
Stent displacement	XX (XX)	XX (XX)	-
Intestinal fistula‡	XX (XX)	XX (XX)	-
Mushroom-shaped tube-related dermatitis	XX (XX)	XX (XX)	-
Mushroom-shaped tube displacement	XX (XX)	XX (XX)	-
Stoma-related complications, No. (%)	XX (XX)	XX (XX)	-

Parastomal hernia	XX (XX)	XX (XX)	-
Dermatitis	XX (XX)	XX (XX)	-
Stoma obstruction	XX (XX)	XX (XX)	-
Stoma bleeding	XX (XX)	XX (XX)	-
Grade of complications			
I	XX (XX)	XX (XX)	XX
II	XX (XX)	XX (XX)	XX
III	XX (XX)	XX (XX)	XX
IV	XX (XX)	XX (XX)	XX
V§	XX (XX)	XX (XX)	XX
Converse to Stent-based Diverting Technique, No. (%)	-	XX (XX)	-
Converse to ileostomy, No. (%)	XX (XX)	-	-
Converse to salvage ileostomy, No. (%)	XX (XX)	-	-
Time of stent degradation			
No stent	XX (XX)	XX (XX)	-
Stent displacement	XX (XX)	XX (XX)	-
Before 3 weeks	XX (XX)	XX (XX)	-
3-4 weeks	XX (XX)	XX (XX)	-
5-6 weeks	XX (XX)	XX (XX)	-
Stoma ending, No. (%)#			
No stoma	XX (XX)	XX (XX)	-
Reversal on time (stage II)	XX (XX)	XX (XX)	-
Delayed reversal	XX (XX)	XX (XX)	-

Table 3

	Stent-based Diverting Technique	Ileostomy	P value
PHS and Costs	n=	n=	
Unplanned readmission, No. (%)	XX ± XX	XX ± XX	XX
PHS (stage I), days	XX ± XX	XX ± XX	XX
PHS (stage II), days	XX ± XX	XX ± XX	XX
PHS (Readmission),	XX ± XX	XX ± XX	XX
Total PHS, days*	XX ± XX	XX ± XX	XX
Total PHS (Only patients with reversal), days*	XX ± XX	XX ± XX	XX
Cost (stage I), CNY	XX ± XX	XX ± XX	XX
Cost (stage II), CNY	XX ± XX	XX ± XX	XX
Cost (Readmission), CNY	XX ± XX	XX ± XX	XX
Total Cost, CNY*	XX ± XX	XX ± XX	XX
Total Cost (Only patients with reversal), CNY*	XX ± XX	XX ± XX	XX
Quality of life	n=	n=	
General Health*	XX ± XX	XX ± XX	XX
Physical Function*	XX ± XX	XX ± XX	XX
Role-Physical*	XX ± XX	XX ± XX	XX
Bodily Pain*	XX ± XX	XX ± XX	XX
Vitality*	XX ± XX	XX ± XX	XX
Social Functioning*	XX ± XX	XX ± XX	XX
Mental Health*	XX ± XX	XX ± XX	XX
Role-Emotional*	XX ± XX	XX ± XX	XX

Subgroup	Level	Events/total SDT	SDT_95%CI	Events/total ILE	ILE_95%CI	RD 97.5%CI	RR	Interaction_p
Age	<60	XX/XX	XX (XX–XX)	XX/XX	XX (XX–XX)	XX (-∞–XX)	XX (XX-XX)	XX
Age	≥60	XX/XX	XX (XX–XX)	XX/XX	XX (XX–XX)	XX (-∞–XX)	XX (XX-XX)	XX
Gender	Female	XX/XX	XX (XX–XX)	XX/XX	XX (XX–XX)	XX (-∞–XX)	XX (XX-XX)	XX
Gender	Male	XX/XX	XX (XX–XX)	XX/XX	XX (XX–XX)	XX (-∞–XX)	XX (XX-XX)	XX
Body_mass_index	<24.0	XX/XX	XX (XX–XX)	XX/XX	XX (XX–XX)	XX (-∞–XX)	XX (XX-XX)	XX
Body_mass_index	≥24.0	XX/XX	XX (XX–XX)	XX/XX	XX (XX–XX)	XX (-∞–XX)	XX (XX-XX)	XX
Diabetes	N	XX/XX	XX (XX–XX)	XX/XX	XX (XX–XX)	XX (-∞–XX)	XX (XX-XX)	XX
Diabetes	Y	XX/XX	XX (XX–XX)	XX/XX	XX (XX–XX)	XX (-∞–XX)	XX (XX-XX)	XX
Noeoadjuvant_radiotherapy	N	XX/XX	XX (XX–XX)	XX/XX	XX (XX–XX)	XX (-∞–XX)	XX (XX-XX)	XX
Noeoadjuvant_radiotherapy	Y	XX/XX	XX (XX–XX)	XX/XX	XX (XX–XX)	XX (-∞–XX)	XX (XX-XX)	XX
Tumor_to_anal_verge	<7	XX/XX	XX (XX–XX)	XX/XX	XX (XX–XX)	XX (-∞–XX)	XX (XX-XX)	XX

Tumor_to_anal_verge	≥ 7	XX/XX	XX (XX-XX)	XX/XX	XX (XX-XX)	XX (-∞-XX)	XX (XX-XX)	XX
Number_of_high_risk_factors	Single	XX/XX	XX (XX-XX)	XX/XX	XX (XX-XX)	XX (-∞-XX)	XX (XX-XX)	XX
Number_of_high_risk_factors	Multiple	XX/XX	XX (XX-XX)	XX/XX	XX (XX-XX)	XX (-∞-XX)	XX (XX-XX)	XX
Prior_abdominal_surgery	N	XX/XX	XX (XX-XX)	XX/XX	XX (XX-XX)	XX (-∞-XX)	XX (XX-XX)	XX
Prior_abdominal_surgery	Y	XX/XX	XX (XX-XX)	XX/XX	XX (XX-XX)	XX (-∞-XX)	XX (XX-XX)	XX
Pathological_T_stage	0-2	XX/XX	XX (XX-XX)	XX/XX	XX (XX-XX)	XX (-∞-XX)	XX (XX-XX)	XX
Pathological_T_stage	3-4	XX/XX	XX (XX-XX)	XX/XX	XX (XX-XX)	XX (-∞-XX)	XX (XX-XX)	XX
Pathological_N_stage	Negative	XX/XX	XX (XX-XX)	XX/XX	XX (XX-XX)	XX (-∞-XX)	XX (XX-XX)	XX
Pathological_N_stage	Positive	XX/XX	XX (XX-XX)	XX/XX	XX (XX-XX)	XX (-∞-XX)	XX (XX-XX)	XX
Centers	Low-volume	XX/XX	XX (XX-XX)	XX/XX	XX (XX-XX)	XX (-∞-XX)	XX (XX-XX)	XX
Centers	High-volume	XX/XX	XX (XX-XX)	XX/XX	XX (XX-XX)	XX (-∞-XX)	XX (XX-XX)	XX

Statistical Analysis Plan (Modified Version 1.1)

Principal Investigator: [name]

Research Institution: Sir Run Run Shaw Hospital, Zhejiang University

Register Number: NCT06204497

Date: 2025-10-06

Version: 1.1

1. Introduction

This trial is a multicenter, prospective, randomized, controlled, open label, parallel-group, non-inferiority trial to evaluate the safety and efficacy of stent-based diverting technique versus ileostomy in rectal cancer patients. In this trial, stent-based diverting technique is considered to reduce the overall length of post-operation hospital stay and medical costs, improve patients' quality of life, while not increasing the peri-operative complication rate. The primary endpoint is the incidence of severe complications within 90-day (Clavien-Dindo \geq III), and the secondary endpoints are the incidence of total complications, the incidence of anastomotic leakage (Grade B/C), and the postoperative hospital stays and cost, and the postoperative quality of life. Patients are randomly assigned into two groups in a 1:1 ratio: stent-based diverting technique receiving rectal cancer surgery followed by stent-based diverting technique, ileostomy group receiving rectal cancer surgery followed by ileostomy. The follow-up period finishes 90 days after the last patient is receiving the final surgery.

2. Population

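### Table 3 plans between-arm P values for total stay and cost in reversed patients only, a post-randomisation subset outside the ITT analysis

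*SAP*

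**What the plan says.** Section 4.7 of the SAP states: "Secondary outcomes will be analyzed in the ITT population". Hospital stay and cost are among the outcomes it lists, to be tested by t-test or Wilcoxon rank-sum test. Section 2.1 groups all randomised patients as assigned, "regardless of whether the allocated intervention was actually received or completed". Section 4.8 names two further populations, PP and AT. None of these is a population of reversed patients.

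The stay-and-cost table in Section 6, headed Table 3, has unrestricted rows "Total PHS, days" and "Total Cost, CNY". Next to them it has "Total PHS (Only patients with reversal), days" and "Total Cost (Only patients with reversal), CNY". All four rows have a cell for each arm and a cell for a P value. The stay-and-cost block has one n per arm. No section of the text defines the reversed subset, says whether it restricts one arm or both, or labels it exploratory.

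**The concern.** Whether and when a stoma is reversed is settled after randomisation. Section 4.6 expects patients in both groups who have no reversal. In the SDT arm a reversal is possible only after conversion to, or salvage by, ileostomy. Selecting on reversal therefore selects different kinds of patient in the two arms, and the protection of randomisation is lost.

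At stake is how the secondary benefits are read. Section 4.6 cites shorter stay and lower cost among the gains that make the non-inferiority margin acceptable. A P value from a selected subset, printed beside the ITT result in the same format, invites the reader to give both the same weight.

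**Working it through.** **No trial figure to reproduce.** The SAP gives no reversal rate, length of stay or cost. The check consists of the two possible readings of the rows and an illustration in which every input is an assumption.

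**The two readings**
- Both arms restricted: the SDT column contains only SDT patients who received an ileostomy and had it reversed. This is a minority if SDT does what it is meant to do.
- Ileostomy arm only restricted: all SDT patients are compared with controls selected on a later event.

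**Inputs (all assumed)**
- s1 = 10 stage I days, the same in both arms
- s2 = 5 or 8 stage II days
- r = 0.80, 0.90 or 0.95, the share of the ileostomy arm reversed
- c = 0.05 or 0.10, the share of the SDT arm with a stoma that was reversed
- d = 0, s2 or 12, the extra stage I or readmission days in unreversed compared with reversed controls

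**Formulas**
- Ileostomy mean, all randomised: s1 + r·s2 + (1 − r)·d
- Ileostomy mean, reversed only: s1 + s2
- Shift caused by the restriction: (1 − r)·(s2 − d)
- SDT mean, all randomised: s1 + c·s2
- SDT mean, reversed only: s1 + s2

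**Shift in the ileostomy mean**
- d = 0: from 0.05 × 5 = +0.25 to 0.20 × 8 = +1.60 days
- d = s2: 0 days
- d = 12: from 0.05 × (8 − 12) = −0.20 to 0.20 × (5 − 12) = −1.40 days

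The sign depends on whether unreversed controls spend fewer or more extra days in hospital than a stage II stay takes. The SAP has nothing on this.

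**SDT minus ileostomy, with s2 = 8, r = 0.90, c = 0.05**

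| Comparison | d = 0 | d = 12 |
|---|---|---|
| All randomised | 10.4 − 17.2 = −6.8 | 10.4 − 18.4 = −8.0 |
| Only ileostomy arm restricted | 10.4 − 18.0 = −7.6 | 10.4 − 18.0 = −7.6 |
| Both arms restricted | 18.0 − 18.0 = 0.0 | 18.0 − 18.0 = 0.0 |

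Restricting controls widens the SDT advantage by 0.8 days when d = 0 and narrows it by 0.4 days when d = 12. Restricting both arms removes it. The exact 0.0 follows from giving both arms the same s1. If converted or salvaged SDT patients stayed longer in stage I, that comparison would favour ileostomy.

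**Missing-data rule.** Section 4.2 leaves patients with missing data out of means and medians. The SAP does not say whether a patient without a stage II admission has a stage II value of 0 or a missing one. If it is treated as missing and carried into the total, these patients would drop out of the unrestricted totals as well.

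**The case against.** The strongest reply is that the restricted rows only supplement the ITT rows. The unrestricted totals are in the same table, each with its own P value cell, so the ITT comparison is not replaced. The rows also have a plausible purpose: Table 2 provides for delayed reversal, and a control whose reversal is pending has an incomplete total, so a completed-pathway figure is informative. The margin is computed as 14% × 0.2 = 2.8% and does not depend on these rows. All of this stands. It limits the weight of the point and supports showing the rows, but it does not support a between-arm test on them.

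The text of the asterisk footnote is not available and might define the subset. The same mark also sits on the unrestricted totals and the quality-of-life rows, however, and no definition would remove the selection on a post-randomisation event.

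Three stronger readings are tempting, and the document does not support them:
- A reader might infer that the rows inflate the ileostomy totals in favour of SDT. That holds only if the ileostomy arm alone is restricted and d is smaller than s2. The other reading pushes the opposite way.
- A reader might infer that the SDT column would hold only failures of the technique. Table 2 lists conversion to ileostomy separately from salvage ileostomy, and Section 2.3 allows for SDT patients having an ileostomy for a variety of reasons.
- A reader might infer that "PHS (stage II), days" and the stage II cost row share the flaw. They carry no restriction label, and with 0 entered where there was no stage II admission they are ordinary ITT components.

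**Conclusion.** The point holds as a minor one. Two planned P values, for total stay and total cost in reversed patients, rest on a subset formed after randomisation that departs from Section 4.7 and is defined nowhere in the text to hand. Under either reading the test is not a randomised comparison.

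Neither the direction nor the size of the bias can be determined from the SAP. The illustrative shifts of −1.40 to +1.60 days in the ileostomy mean, and the differences of −7.6 or 0.0 days against −6.8 in all randomised patients, rest wholly on assumed inputs. They show only that the result depends on an unstated definition. No figure for cost is offered, because the SAP gives no split between stage I and stage II cost. The primary analysis and the non-inferiority conclusion are not affected.

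**What to change.** - Remove the P values from the two reversal-only rows of Table 3 and present them descriptively. State which arm or arms the restriction applies to.
- Give these rows their own n per arm, with the number never reversed and the number with reversal pending.
- Keep the ITT rows for total stay and total cost as the tested comparison. State in Section 4.2 or 4.7 that stage II counts as 0 where no stage II admission occurred, so that these patients are not dropped as missing.

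The cost is a change to SAP wording and one table shell, with no new data. There are two downsides. The completed-pathway comparison is no longer formally tested. Patients with reversal still pending contribute an incomplete total to the ITT rows, which should be noted beside the result.
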